1.0 PROTOCOL SUMMARY AND/OR SCHEMA

[figure not shown]
This is a two-arm, parallel, open-label, phase II clinical trial designed to assess the efficacy and safety of atezolizumab alone and of atezolizumab in combination with low-dose local radiotherapy in patients with relapsed or refractory follicular lymphoma.

Fifty patients will be enrolled at an estimated accrual rate of 3 patients per month, and will be randomly assigned to receive atezolizumab alone or atezolizumab and local, low-dose radiotherapy.

See Figure 1 for Study Schema.

Figure 1: Study Schema

Subject Randomly Assigned to Treatment Arms

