14.0 BIOSTATISTICS

14.1 Determination of Sample Size

To accomplish our primary objectives we will use a randomized parallel 2-arm 1-stage design. All patients will be randomly assigned to one of the two treatment arms, and each arm will be monitored and analyzed separately. For both arms, a 43% or higher response rate is considered promising, whereas a 20% or lower is considered not promising.

Novel therapies [e.g. bortezomib or lenalidomide] have single agent ORR of ~20% in relapsed/refractory FL [Goy 2005, Witzig 2009, Di Bella 2010] and are highly active in combination [e.g. when combined with the anti-CD20 monoclonal antibody rituximab]. These data suggest that excluding an ORR <20% while targeting an ORR >43% would be a conservative approach to evaluation of atezolizumab treatment effect as a single agent or in combination with low dose local radiotherapy in this population of patients with relapsed/refractory FL. To this end for each arm, a total of 25 patients will be accrued (once one arm reaches the enrollment goal of 25, randomization will stop and all the future patients will be automatically assigned to the other arm).

If 8 or fewer patients in either treatment arm respond, that treatment will be considered not promising. If 9 or more patients respond in either treatment arm, then that arm will be declared promising and worthy of further investigation.

This 1-stage design has type 1 and 2 error rates at 0.05 and 0.2, respectively. Given this design we may stop either arm early if we have observed 17 or more non-responders. If both arms are declared desirable by demonstrating 9 or more responses in their 25-patient cohorts, we will use the pick-the-winner approach as a general principle where the choice of which arm will be suitable for further study will be based on the absolute number of responses. If the treatment arm with a higher number of responses is also associated with more toxicity, then the investigators will weigh both the absolute number of responses and toxicity in selecting which arm is suitable for further study. If the difference in the true response rates of the treatment arms is 10% (i.e. 43% vs 53%) then the chance that the regimen with the higher response rate will be picked is over 70%. If the difference in the true response rates of the treatment arms is 15% (i.e. 43% vs 58%) then the chance that the regimen with the higher response rate will be picked is over 80%.

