14.6 Method of Analysis for Correlative Endpoints

Objective response rates, progression-free survival, and overall survival will be estimated for patients with preexisting tumor antigen restricted tumor infiltrating lymphocytes (TILs) and patients without preexisting tumor antigen restricted (TILs), and for patients who demonstrate a 2-fold expansion of T cell receptor (TCR) clonality and patients who do not demonstrate a 2-fold expansion of TCR clonality, and groups will be compared using Fisher's exact tests (ORR) and logrank tests (PFS and OS). Similar comparison will be performed to associate other biomarkers described in 2.3

with the outcomes. To assess the impact of treatment on peripheral blood cytokine/chemokine levels, Wilcoxon signed rank test will be used to test the intra-patient changes in these factors.

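### For associations with ORR, PFS and OS, section 14.6 plans only group comparisons of biomarkers, many of them continuous, and states a numeric cut for TCR clonality alone; adding continuous tests would be a cheap improvement.

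*Combined protocol and SAP*

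**What the plan says.** Section 14.6 (Method of Analysis for Correlative Endpoints) forms two pairs of groups. The first is "patients with preexisting tumor antigen restricted tumor infiltrating lymphocytes (TILs) and patients without preexisting tumor antigen restricted (TILs"). The second is "patients who demonstrate a 2-fold expansion of T cell receptor (TCR) clonality and patients who do not demonstrate a 2-fold expansion of TCR clonality". The method is then: "groups will be compared using Fisher's exact tests (ORR) and logrank tests (PFS and OS"). For everything else it says "Similar comparison will be performed to associate other biomarkers described in 2.3" with the outcomes.

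The 2-fold figure is the only numeric cut. Sections 2.3 and 12.2 and Appendix 9 give no other cut, no rule for choosing one, and no analysis of a continuous marker against an outcome. Section 12.2.2 lists 13 IHC antibodies and several T-cell subsets measured by flow cytometry.

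One analysis in 14.6 splits nobody: the effect of treatment on cytokine and chemokine levels is tested by a Wilcoxon signed rank test on within-patient change. Section 2.3 classes all these aims as exploratory.

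**The concern.** Fisher's exact and log-rank tests need groups. Applying a similar comparison to a flow percentage, a staining density or a cytokine level therefore implies splitting it. A split treats a patient just above the cut like one far above it. If risk or response changes gradually with the marker, that ordering is information, and the sample is small: "Fifty patients will be enrolled at an estimated accrual rate of 3 patients per month". Fewer will have paired tumor samples, because section 10.1 asks for the Cycle 2 biopsy only where clinically feasible.

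The second issue is the unstated cut. In an open-label trial, with no cut written down, nothing prevents one being picked after responses are known. At stake is how reliable and how sensitive the exploratory findings are, not the arm-level decision.

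**Working it through.** **1. The plan's own figures.** Section 14.6 states no sample size, alpha or power. The nearest figures are for the primary rule in 14.1: "For both arms, a 43% or higher response rate is considered promising, whereas a 20% or lower is considered not promising"; "If 9 or more patients respond in either treatment arm, then that arm will be declared promising"; "This 1-stage design has type 1 and 2 error rates at 0.05 and 0.2, respectively". Exact binomial, n = 25:
- P(X ≥ 9 | 0.20) = 0.047
- P(X ≥ 9 | 0.43) = 0.818, so the type 2 error is 0.182

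These reproduce the stated limits. They do not cover the biomarker tests.

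**2. Response: assumptions.** The documents give no marker distribution and no expected share reaching 2-fold. Assumed: marker (or log fold-change) normal with SD 1; responders shifted by 0.8 SD; two-sided 0.05. Group sizes are 20 and 30 (40% of 50, near the 43% target), or 15 and 25 as an illustration of fewer paired samples. The cut is placed so that a share q = 15-50% of non-responders lies above it. The share of responders above the cut is then 1 − Φ(z − 0.8), where z is the upper-q normal point:
- q = 15%: 1 − Φ(1.036 − 0.8) = 41%
- q = 50%: 1 − Φ(0 − 0.8) = 79%

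**3. Response: results.** Power of Fisher's test on those two proportions, against Wilcoxon rank-sum on the unsplit marker:

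| Responders / non-responders | Wilcoxon | Fisher at the cut |
|---|---|---|
| 20 / 30 | 74-77% | 45-56% |
| 15 / 25 | 61-64% | 35-41% |

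The ranges cover the cut positions and repeated simulations. Exact enumeration of Fisher power at 20/30 gives 46.5% (q = 15%), 55.5% (q = 30%) and 50.5% (q = 50%).

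**4. Response: sensitivity.** N = 50, shift set so that a t-test on the continuous marker has 80% power:

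| ORR | Wilcoxon | Fisher: median split | top 25% | top 20% | top 10% |
|---|---|---|---|---|---|
| 43% | 77% | 53% | 47% | 38% | 22% |
| 20% | 75% | 44% | 58% | 58% | 45% |

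**5. PFS and OS.** For a log-linear effect, the efficiency of a split with share q above the cut is φ(z)² / [q(1 − q)]. If the continuous test has 80% power, power after the split is Φ(√efficiency × (1.960 + 0.842) − 1.960).
- Median: 0.1592/0.25 = 0.637, power 61%, equivalent to 0.637 × 50 ≈ 32 patients
- Top 25%: 0.539, 54%, about 27 patients
- Top 20%: 0.490, 50%, about 25 patients
- Top 10%: 0.342, 37%, about 17 patients

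**6. The reverse case.** Suppose response is 75% above the cut and 25% below it, flat on each side, N = 50:

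| Share above the cut | Fisher | Wilcoxon |
|---|---|---|
| 20% | 79-80% | 53-55% |
| 30% | 88-89% | 75% |
| 50% | 95% | 87-89% |

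Here the split wins.

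**7. If a cut were chosen by outcome.** Null marker, N = 50, each group at least 10, so 40 − 10 + 1 = 31 candidate cuts, keeping the smallest p-value. P(p < 0.05) is about 23-25% for Fisher and 29-32% for log-rank (the lower figure assumes about 30% censoring). Scanning the middle 80% of values instead gives 26-28% for Fisher.

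**The case against.** The strongest objection is that the power loss depends on the model. A normal shift favours a rank test; under a threshold effect at the chosen cut the order reverses (step 6). The documents support neither shape over the other. This stands, so the loss can be claimed only conditionally. Groups also give directly readable response rates and Kaplan-Meier curves, which is a fair reason to keep the 2-fold comparison.

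A reader might also infer more than the text supports:
- *That every biomarker is tested by splitting patients.* Cytokine and chemokine change is not. TIL presence and MRD may be natural yes/no measures, for which nothing is lost. For the remaining markers the split is implied by a loose phrase, not written out.
- *That cuts will have to be chosen once outcomes are known.* Silence allows this but does not require it. A median or an assay threshold could be fixed blind to outcome. No scan is planned, and the 23-32% figures do not apply to the prespecified 2-fold cut.
- *That a stated 5% level is exceeded.* Section 14.6 states no alpha; the 0.05 in 14.1 belongs to the primary rule. Five percent here is only the conventional benchmark.

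Exploratory status limits the consequence. It is not a reason to set aside ordering information in a small sample, or to leave cuts open.

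**Conclusion.** The point holds as a modest improvement to the correlative analysis. For associations with ORR, PFS and OS, only group comparisons are planned, one numeric cut is given, and no continuous analysis backs them up. Under a smooth effect the cost is roughly 20-30 percentage points of power in the 20/30 and 15/25 settings. It ranges from 17 to 55 points across the wider set of cuts and response rates in step 4, and from 19 to 43 points for survival. These figures rest on an assumed normal marker, the assumed shift and the assumed group sizes; under a true threshold the split is better. The false-positive figure of roughly 23-32% per marker describes what the open wording would allow, not what the plan proposes. The primary ORR decision is untouched.

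**What to change.** In 14.6:
- Make the main test for each continuous marker a Wilcoxon rank-sum test of the marker (or its log fold-change) by response, and a Cox regression on the log-transformed marker for PFS and OS.
- Keep the prespecified 2-fold TCR groups as a secondary or descriptive analysis.
- Leave naturally binary markers (TIL presence, MRD) and the cytokine signed rank analysis as they are.
- State that any other cut, or the rule for setting it, will be fixed without reference to outcome data.

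The cost is a few sentences and trivial programming, with no new samples, visits or patients. The downside is that the Cox model assumes a log-linear effect, and a rank or continuous test is weaker if the true effect is a threshold. Retaining the 2-fold comparison covers that case for TCR clonality.

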2.3 Exploratory Objectives

To determine if clinical responses to atezolizumab are associated with preexisting tumor antigen restricted effector T cells or the development of a more clonal T-cell receptor (TCR) repertoire, and we will determine what impact the addition of concurrent local, low-dose radiotherapy has on TCR diversity and clinical responses.

Using immunohistochemistry, multiplex immunofluorescence, and fresh tissue immunophenotyping with pre-treatment and on-treatment tissue samples and peripheral blood, aim to assess biomarkers related to PD-L1 and/or immune cell biology and tumor biology that might contribute to our understanding of the mechanism of response to PD-L1 therapy and of the abscopal effect of radiation therapy in follicular lymphoma.

Perform a preliminary assessment of the prognostic value of minimal residual disease (MRD).

To determine what impact treatment with atezolizumab and the addition of concurrent local, low-dose radiotherapy has on peripheral blood cytokine/chemokine levels.

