There is a need for novel combination strategies to augment the activity of PD-1/PD-L1 blockade in FL. In addition to its direct cytotoxic effects, radiotherapy (RT) initiates immunogenic cell death of tumor cells via multiple mechanisms. RT leads to the release of tumor antigen into the TME, translocation of calreticulin to the tumor cell membrane, and release of endogenous adjuvants (e.g. HMGB1, uric acid, heat shock proteins), which in turn lead to the recruitment of dendritic cells, cross presentation of tumor antigens by dendritic cells, and cross priming of tumor CTLs [Vatner et al, 2014].

The combination of RT and either PD-1 or PD-L1 blockade is synergistic in mouse models of colorectal cancer, melanoma, and breast cancer, with improved tumor control and survival, and induction of a durable tumor-specific response and resistance against tumor re-challenge [Dovedi et al, 2014]. Because concurrent RT and PD-1/PD-L1 blockade resulted in synergistic effect on survival whereas sequential therapy did not (RT administered 5 or 7 days prior to PD-1/PD-L1 blockade) [Dovedi et al, 2014], investigators testing the combination of RT and immune checkpoint blockade should limit the time interval between RT and the initiation of immune checkpoint blockade. The addition of local RT to CTLA4 blockade increased the density and diversity of tumor antigen restricted CTLs in a breast cancer mouse model [Pilones et al, 2015].

Low-dose local radiotherapy (RT) with 4Gy in 2 fractions induces durable local disease control without significant toxicity [Hoskin et al, 2014], and has been shown to induce an abscopal effect in patients with FL, with patients treated with the intratumoral TLR9 agonist CpG inducing circulating tumor reactive CTLs and achieving responses at distant sites only with concomitant low-dose irradiation [Brody et al, 2010]. This dose and fractionation of RT is therefore safe and sufficient to induce a systemic immune response in patients with relapsed/refractory, advanced stage FL.

We therefore hypothesize that a radiotherapy-induced systemic immune response can augment atezolizumab activity in patients with advanced stage FL.

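### Section 14.6 names no arm factor in its biomarker tests, so for on-treatment markers a pooled test can mistake an effect of radiotherapy for a marker association, or hide a real one

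*Combined protocol and SAP*

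**What the plan says.** Section 14.6 (Method of Analysis for Correlative Endpoints) forms two pairs of groups and compares response, PFS and OS between them. One grouping is fixed before treatment: "patients with preexisting tumor antigen restricted tumor infiltrating lymphocytes (TILs") against those without. The other is observed after treatment starts: "patients who demonstrate a 2-fold expansion of T cell receptor (TCR) clonality" against those who do not. The comparisons use Fisher's "exact tests (ORR) and logrank tests (PFS and OS). Similar comparison will be performed to associate other biomarkers described in 2.3". No arm factor and no significance level are given.

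Other sections do mention arm. Section 14.5 describes response rates by assigned arm, and Section 14.4 tabulates toxicity by cohort. Section 14.1 says that "each arm will be monitored and analyzed separately", but in a passage that opens by referring to the primary objectives.

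On what radiotherapy may do, Section 2.3 states that "we will determine what impact the addition of concurrent local, low-dose radiotherapy has on TCR diversity and clinical responses". Section 3.2 ends its rationale with: "We therefore hypothesize that a radiotherapy-induced systemic immune response can augment atezolizumab activity in patients with advanced stage FL".

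**The concern.** The plan supplies both links needed for confounding by arm. It hypothesises that radiotherapy raises activity, and it treats an effect of radiotherapy on the T-cell repertoire as an open question worth studying. If both effects exist, arm is a common cause of on-treatment expansion and of outcome. Pooling then places more radiotherapy patients in one marker group, and their different response rate is credited to the marker.

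At stake is the exploratory aim of learning whether response goes with a more clonal repertoire. Section 2.3 lists that aim separately from the effect of radiotherapy on repertoire and response. A pooled test mixes the two.

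Biopsy location may add a more direct route from arm to marker. Section 10.1 aims to take the pre-treatment sample from the site to be irradiated and the on-study sample from the same place. Footnote f of Appendix 1 wants biopsies outside the radiation field. The two need to be reconciled. Under the former, the radiotherapy arm's tissue marker would come from irradiated tissue.

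**Working it through.** **Inputs from the plan.** Per arm, "a total of 25 patients will be accrued" (Section 14.1). Reference rates: "For both arms, a 43% or higher response rate is considered promising, whereas a 20% or lower is considered not promising". The only between-arm gaps that the plan states are 43% vs 53% and 43% vs 58% (Section 14.1).

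**Assumptions.** Expansion rates by arm, PFS medians and hazard ratios are not in the documents, so a range is shown. The level is taken as two-sided 0.05. Marker and outcome are independent within each arm, so every rejection is a false positive.

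**Plan's own figures.** Section 14.6 has none to reproduce. Those of Section 14.1 do reproduce: with X ~ Bin(25, p), P(X ≥ 9) is 0.0468 at p = 0.20 and 0.818 at p = 0.43 (stated: type 1 error 0.05, type 2 error 0.2). The chance that the better arm has strictly more responses is 0.716 (43% vs 53%) and 0.824 (43% vs 58%), matching the stated figures of over 70% and over 80%.

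**Pooled odds ratio.** Let q be the expansion rate and r the response rate, with subscript A for atezolizumab alone and R for the radiotherapy arm. With equal arms:

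- response in expanders = (q_A r_A + q_R r_R) / (q_A + q_R)
- response in non-expanders = ((1 − q_A) r_A + (1 − q_R) r_R) / (2 − q_A − q_R)

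For r = 20%/43% and q = 20%/60%:

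- expanders: (0.04 + 0.258)/0.8 = 0.3725
- non-expanders: (0.16 + 0.172)/1.2 = 0.2767
- odds ratio: (0.3725/0.6275)/(0.2767/0.7233) = 1.55, although it is 1 in each arm

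**Rejection rates for response.** 40,000 simulated trials per row, 25 per arm. The Monte Carlo standard error at a 10% rate is √(0.1 × 0.9/40,000) = 0.15 percentage points.

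| ORR, A / R | Expansion, A / R | Pooled OR | Pooled Fisher | Arm-stratified exact |
|---|---|---|---|---|
| 43% / 58% | 40% / 40% | 1.00 | 3.7% | 3.7% |
| 43% / 53% | 30% / 50% | 1.09 | 4.0% | 3.7% |
| 43% / 53% | 20% / 60% | 1.18 | 4.6% | 3.4% |
| 43% / 53% | 10% / 90% | 1.38 | 6.5% | 2.1% |
| 43% / 58% | 20% / 60% | 1.28 | 5.5% | 3.3% |
| 43% / 58% | 10% / 70% | 1.46 | 7.8% | 3.0% |
| 43% / 58% | 10% / 90% | 1.62 | 10.7% | 2.1% |
| 20% / 43% | 30% / 50% | 1.25 | 5.0% | 3.4% |
| 20% / 43% | 20% / 60% | 1.55 | 8.6% | 3.1% |
| 20% / 43% | 10% / 70% | 1.93 | 15.6% | 2.9% |
| 20% / 43% | 10% / 90% | 2.39 | 23.0% | 2.0% |

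The first row is the baseline: with equal expansion in the two arms there is no confounding, and Fisher's test runs at 3.7% because it is conservative.

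**Opposite direction.** Reverse the expansion rates to 60%/20% and keep response at 20%/43%. Expanders respond at (0.12 + 0.086)/0.8 = 0.2575 and non-expanders at (0.08 + 0.344)/1.2 = 0.3533. The pooled odds ratio is (0.2575/0.7425)/(0.3533/0.6467) = 0.63. A true positive within-arm association would be pulled towards 1 or below.

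**PFS.** 8,000 simulated trials per case, with an assumed 10-month median on atezolizumab alone and censoring at 24 to 41 months. With an arm hazard ratio of 0.67, the pooled logrank rejects 8.4% (expansion 20%/60%) and 12.2% (10%/70%). With 0.5 it rejects 13.4% and 23.7%. The arm-stratified logrank rejects 5.0% to 5.7% in these four cases. OS was not computed.

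**Fewer samples.** On-treatment biopsies are taken only where feasible (Section 10.1). With 18 per arm, response 20%/43% and expansion 20%/60%, pooled Fisher rejects 6.2% and the stratified test 2.9%.

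**The case against.** Pooling is never stated. It is inferred from silence, and Section 14.1 does speak of separate analysis. That sentence concerns the primary design, so it does not settle the matter. If within-arm tests are intended, each has at most 25 patients and Section 14.6 should say so.

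The inflation is modest at the gaps the plan itself gives. With 20%/60% expansion, pooled Fisher rejects 4.6% or 5.5%, against about 3.7% without confounding. The 20% vs 43% gap sets the null rate of a single-arm test against its target rate; the plan does not present it as an expected difference between arms. This stands and limits the size of the point.

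A reader might infer that every biomarker test in Section 14.6 is biased. The documents do not support that. Pre-existing TILs and other pre-treatment markers are fixed before treatment and balanced in expectation by the randomisation in Section 15.2.

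A reader might also infer that the bias always creates a false positive. The direction is open. Section 3.2 cites a mouse model in which radiotherapy added to CTLA-4 blockade increased T-cell diversity; if that means less clonality here, the bias could mask an association. If radiotherapy works through expansion, a real within-arm association would exist, and a stratified test addresses that directly.

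Finally, these analyses are exploratory, with no stated level or decision attached. That is correct and sets the weight of the point.

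**Conclusion.** The concern holds in a limited form. Section 14.6 names no arm factor, and its natural reading pools the arms. For on-treatment markers the pooled Fisher and logrank tests are open to confounding by arm if radiotherapy affects both marker and outcome, which the plan regards as plausible.

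Under within-arm independence with 25 per arm, the false-positive rate for response is about 4% to 11% at the plan's own between-arm gaps. It is about 9% to 23% at 20% vs 43% with expansion rates from 20%/60% to 10%/90%. Stratification by arm gives about 2% to 4%. All expansion rates, and all PFS inputs, are assumptions.

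It would go too far to say that the pooled tests will report a spurious association: even in the most extreme response scenario shown, 77% of trials would not (100% − 23.0%). The rule of 9 or more responses in 25 and the choice between arms do not depend on this analysis.

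**What to change.** In Section 14.6, state that tests of on-treatment markers against outcome are stratified by randomised arm: an exact stratified or Mantel-Haenszel test for response, and a stratified logrank test for PFS and OS. Show arm-specific estimates beside each. The same may be applied to baseline markers for consistency, though bias does not require it there.

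This is a free improvement. It needs one or two sentences in the plan and a stratum term in the code, with no new patients or data. One limit should be accepted: where marker status nearly coincides with arm, the stratified test becomes conservative (about 2% at 10%/90% expansion), because such data hold little information to separate marker from arm.
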